## 5.2 Study Visits

### 5.2.1 *Procedures Before Study Treatment*

All efficacy and safety assessments to be performed during the pre-treatment period are indicated in [Table 2](#) (please see footnotes in the table for details) and described in [Section 7](#) and [Section 8](#), respectively.

A signed and dated informed consent form may be obtained more than 15 days prior screening but must be provided before any study-specific procedures are performed. However, evaluations performed as part of routine care prior to the date of the signed informed consent form can be used as Screening evaluations if permitted by the IRB/Ethics Committee (EC) policies of the investigational site. Subjects will acknowledge and agree to the possible use of these data in the study by signing the informed consent form.

All screened subjects will be allocated a subject number so that they can be identifiable throughout the study. The Investigator will maintain a list of screened subjects (i.e. who signed the informed consent form), subject numbers and names to ensure that all records may be found at a later date if required. In case a subject does not receive cabozantinib after the Screening visit, the primary reason will be recorded.

### 5.2.2 *Procedures During Study Treatment*

All efficacy and safety assessments to be performed throughout the treatment period are indicated in [Table 2](#) (please see footnotes in the table for details) and described in [Section 7](#) and [Section 8](#), respectively.

Clinical status will be evaluated by the Investigator at each visit to the investigational site to confirm that the subject is suitable to continue study treatment and to make timely decisions regarding the interruption or restart of cabozantinib dosing. Tumour assessments from imaging visits will be reviewed by central review and by the local Investigator.

Subjects may discontinue study treatment any time during the study due to reasons such as disease progression, intolerance to cabozantinib, need for subsequent systemic investigational drug therapy or other reasons for study treatment discontinuation listed in this protocol ([Section 4.3.1](#)). This implies that the duration of cabozantinib treatment may be different for each subject included (see [Section 3.6](#) for details), but the study is planned to follow-up subjects up to 18 months after the last subject included in the study received the first cabozantinib dose.

Subjects with radiographic progression per RECIST 1.1 evaluated by the Investigator may continue study treatment if the Investigator believes that there still is clinical benefit and that it outweighs potential risks. In this case, study treatment can be continued up to the end of the study ([Section 5.6](#)), unless the subject or the Investigator decides to discontinue study treatment due to unacceptable toxicity or needs subsequent systemic anti-cancer treatment.

Subjects who discontinue study treatment with cabozantinib (e.g. due to radiographic progression or unacceptable toxicity) will be invited to attend the End of Study Treatment visit ([Section 5.2.2.1](#)).

Subjects who discontinue study treatment due to withdrawal of consent will be invited to attend the Early Study Withdrawal visit ([Section 5.2.2.2](#)).

### 5.2.2.1 *End of Study Treatment Visit*

The End of Study Treatment visit will be carried out 30 to 45 days after the last cabozantinib dose (all necessary assessments to be performed at this visit are indicated in [Table 2](#)). After this date, the subject will enter the Post-treatment Follow-up period ([Section 5.2.3.1](#)).

The Investigator will ask subjects to return any remaining cabozantinib tablets and check their compliance to study protocol. Efficacy evaluations should not be performed for subjects who do not attend the End of Study Treatment visit within 30 to 45 days after their last dose of cabozantinib. Subjects with ongoing AEs or clinically significant laboratory test abnormalities (as determined by the Investigator) will be monitored as described in [Section 8.1.3](#) and [Section 8.1.2.4](#), respectively.

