g Microscopic urine examination to be performed at baseline and after that only at the discretion of the Investigator (results are not to be collected in the eCRF except in case of clinically abnormal findings, which are to be reported as an AE). Urine chemistry (24-hour urine protein or UPCR) may be performed at any scheduled or unscheduled visit at the discretion of the Investigator and based on results of routine urinalysis or as clinically indicated.

CONFIDENTIAL

FINAL PROTOCOL (INCLUDING AMENDMENT #4): 23 FEBRUARY 2022PAGE 49/228

h Follow-up for radiographic progression, tumour assessment should be performed until radiographic progression confirmed by the Investigator only for subjects who have discontinued cabozantinib treatment before radiographic disease progression and who have not withdrawn consent.

 Cabozantinib will be self-administered at home until study treatment is discontinued.

j Information on new or worsening AEs will be collected from date of the signed informed consent until the end of study treatment, at each study visit, by telephone call or by spontaneous report by the subject. Any AEs and SAEs that are ongoing 30 days after the date of the last cabozantinib dose are to be followed until resolution or until the Investigator considers the event is stable or irreversible (see [Section 8.1.3](#)).

k During the follow-up period, any SAEs that occur more than 30 days after the date of the last cabozantinib dose, assessed as related to study treatment or study procedures will also be collected and followed until resolution or stability according to the Investigator.

l Information on prior and concomitant medication will be collected up to 30 days before baseline until 30 days after the date of the last cabozantinib dose.

m *The FACIT and all related works are owned and copyrighted by, and the intellectual property of [name]. Permission for use of the FCSI-DRS questionnaire is obtained by contacting [name] at [[contact]](mailto:[contact]).*

Based on an average treatment duration of 8 months and 12 visits, the total volume of blood drawn for all evaluations throughout this study will be approximately 144 mL for each subject (12 mL of blood per visit, this volume may depend on the laboratory used, treatment duration and number of visits).

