### 5.2.3 *Procedures After Study Treatment*

Subjects who discontinue study treatment with cabozantinib will be invited to enter the Post-treatment Follow-up period. All necessary assessments performed after treatment are indicated in [Table 2](#).

For subjects who have discontinued cabozantinib treatment before radiographic disease progression and who have not withdrawn consent, tumour assessment should be performed until radiographic progression confirmed by the Investigator.

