#### 7.3.1 Tumour Assessments

Radiographic tumour assessments will include contrast tomography (CT) and/or magnetic resonance imaging (MRI) scans of the chest, abdomen, pelvis (C/A/P), brain, and bone scintigraphy scans. The same imaging modalities used at the Screening visit should be used for subsequent tumour assessments. For subjects who have discontinued cabozantinib treatment before radiographic disease progression and who have not withdrawn consent, tumour assessment should be performed until radiographic progression is confirmed by the Investigator. (see [Table 2](#) for schedule of assessments).

Tumour assessments will determine the study endpoints of ORR, TTR, DOR, DCR, and PFS. The review of radiographic images will be conducted by a blinded, central IRC ([Section 3.8](#)) by batch using RECIST 1.1 (see IRC charter). All radiographic tumour assessments (both scheduled and unscheduled) must be sent to the IRC. Prior radiation history data will also be reviewed by the IRC for selection of target lesions.

Radiographic response and disease progression according to Investigator's assessment will also be assessed by the local Investigator using RECIST 1.1 (see [Appendix 5](#)) for subject management and treatment decisions.

All CT/MRI scans (C/A/P, brain) and scintigraphy scans (bone) are recommended to be performed using the study-specified imaging protocol (refer to the most recent version of the

imaging manual). To ensure image consistency, the same imaging modalities and acquisition protocols used at the Screening visit should be used for subsequent tumour assessments.

If any doubt or ambiguities exist about radiographic progression, the Investigator is encouraged to continue study therapy if the subject presents acceptable tolerance and repeat the radiographic studies at the next scheduled time, thus delaying the determination of progression until the findings indicating radiographic progression are unequivocal. Radiographic progression determined by the Investigator does not warrant discontinuation of tumour assessments or study treatment (see [Section 5.2.2](#)).

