1.3 Methods and procedures

1.3.1 *Subject identification and allocation to study treatment*

In this study, data will be collected through an eCRF. Once the subject has provided his/her informed consent, the eCRF will provide a numeric subject identifier to pseudonymise the data within eCRF. Only investigating sites will be able to link to numeric identifier to the subject.

Each subject will only be given the study treatment if they carry his/her registration number. At each cabozantinib dispensation (at scheduled and unscheduled visits, if applicable), treatment number(s) will be assigned by the Interactive Web Response System (IWRS), according to the appropriate dose (dose adaptation).

1.3.2 *Subjects assessments*

1.3.2.1 *Efficacy assessments*

The timing of efficacy assessments is provided in [Table 2](#).

The primary and secondary efficacy endpoints are detailed in Section [3.1.1](#) and Section [3.1.2](#), and the statistical methods to be used in the analysis of these efficacy endpoints are provided in Section [3.2.1](#).

Tumour Assessments

Radiographic tumour assessments will include contrast tomography (CT) and/or magnetic resonance imaging (MRI) scans of the chest, abdomen, pelvis (C/A/P), brain and bone scintigraphy scans. The same imaging modalities used at the Screening visit should be used for subsequent tumour assessments.

C/A/P CT/MRI will be performed at Screening/Baseline (within 28 days prior start of study treatment) and then every 12 weeks (± 10 days) while on study protocol treatment beginning at Week 12 (i.e. Week 12, Week 24, Week 36, etc) until the end of study. There could be additional assessments if clinically indicated. Follow-up for radiographic progression, tumour assessment should be performed until radiographic progression confirmed by the Investigator for subjects who have discontinued

SAP Final: Version 6.0: 17 August 2023

cabozantinib treatment before radiographic disease progression and who have not withdrawn consent.

Brain CT/MRI and Bone scintigraphy scan will be performed at Screening/Baseline (within 28 days prior start of study treatment) only if they are indicative of metastases. Then they will be performed at same timepoints only if there are brain and/or bone metastases at screening or if there are signs or symptoms suggesting that metastases develop.

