In case of non-censoring and a partial progression/death date, missing day will be imputed by the first day of the month. This will be the most conservative approach considering that the earliest date for progression/date. It will be imputed by the date of initial response in case the date of initial response is later than the imputed date.

In case of censoring and a partial last tumour assessment date, missing day will be imputed by the first day of the month. It will be imputed by the date of initial response in case the initial response is later than the imputed date. The censoring may occur earlier than the exact date.

(4) Time-to-Progression for Progression-Free Survival (PFS) analysis

PFS is defined as the time from start of study treatment to either disease progression (as determined by independent central review per RECIST 1.1) or death due to any cause, whichever occurs first. For subjects who are not known to have died or progressed at the time of data cut-off for PFS analysis, the PFS will be censored at the last tumour assessment and considering the censoring rules defined in the table below.

| Event | Decision | Date of event or censoring |
|---|--------------|---|
| Progressive disease with no more than one missing scheduled tumor assessment before the event and without NPACT before the event. | Not censored | Date of first progressive disease |
| Death with no more than one missing scheduled tumor assessment before the event and without NPACT before the event. | Not censored | Date of death |
| PD or death with two or more missing scheduled tumor assessments before the event | Censored | Date of the last tumor assessment prior to the missing assessment. |
| PD or death with NPACT after the start of cabozantinib and before the event | Censored | Date of the last tumor assessment prior to the date of initiation of NPACT. |
| No event (no PD, no death) with at least one radiological | Censored | Date of last radiological assessment |

SAP Final: Version 6.0: 17 August 2023

| | | |
|---|----------|-----------------------------------|
| assessment after the initiation of study treatment. | | |
| No event (no PD, no death) without any radiological assessment after the initiation of study treatment. | Censored | Date of first cabozantinib intake |

PFS will be calculated as:

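### Protocol 5.2.2.1 bars efficacy evaluations after a missed End of Study Treatment visit, while 5.2.3, 7.3.1 and Table 2 require imaging until progression; the rules need reconciling to protect PFS and DOR

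*Protocol*

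**What the plan says.** Protocol 5.2.2.1 describes the End of Study Treatment visit, held 30 to 45 days after the last dose. It contains the instruction "Efficacy evaluations should not be performed for subjects who do not attend the End of Study Treatment visit within 30 to 45 days" after that dose. The sentence carries no qualification and no exception for follow-up scans.

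Three other places in the protocol set the imaging rule for subjects who stopped cabozantinib before radiographic progression and have not withdrawn consent:

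- Section 5.2.3: "tumour assessment should be performed until radiographic progression confirmed by the Investigator".
- Section 7.3.1: "tumour assessment should be performed until radiographic progression is confirmed by the Investigator".
- Table 2, footnote h: "tumour assessment should be performed until radiographic progression confirmed by the Investigator only for subjects who have discontinued cabozantinib treatment" before progression.

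The SAP repeats this imaging rule in 1.3.2.1 and in footnote h of its own Table 2. It does not repeat the bar. Attendance at the visit is by invitation: under Protocol 5.2.2, subjects who stop treatment "will be invited to attend the End of Study Treatment visit".

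**The concern.** A subject can stop treatment before progression, keep consent in force, and be seen late or not at all for the End of Study Treatment visit. That subject falls under both instructions. One tells the site to do no efficacy evaluations; the other tells it to keep scanning. Neither document ranks them.

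PFS and DOR are at stake. Both take their progression dates from scans, and both are censored at the last tumour assessment when no event is recorded. The DOR estimand also labels discontinuation before progression as treatment policy, which needs scans after stopping. If sites resolve the conflict differently, follow-up for these endpoints will depend on the site's reading of one sentence.

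**Working it through.** The plan states no figure on this point, so there is none to reproduce. The check compares the texts, follows the consequence through the SAP's censoring rules, and sizes it under stated assumptions.

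**1. Does the barred activity include imaging?** Yes, on the protocol's own usage. Section 3.1 says that the efficacy evaluations include the radiographic tumour assessments, and 7.3.1 sits within the section on assessment of efficacy. Read as written, the bar in 5.2.2.1 covers scans.

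**2. Do the rules apply to the same subjects?**

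| | 5.2.2.1 | 5.2.3, 7.3.1, footnote h |
|---|---|---|
| Who | Subjects not attending within 30 to 45 days of last dose | Subjects who stopped before radiographic progression, consent not withdrawn |
| Instruction | No efficacy evaluations | Tumour assessment until progression |
| Depends on the visit? | Yes | No |

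The groups overlap in consenting subjects who stopped before progression and missed the window. For them the instructions are opposite.

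**3. What follows under the SAP, Appendix 1?** Without an event, "the PFS will be censored at the last tumour assessment", and DOR follows the same pattern. For "PD or death with two or more missing scheduled tumor assessments before the event", the subject is censored at the last scan before the gap. A death with no more than one scheduled scan missed and no prior non-protocol anti-cancer therapy still counts as an event.

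**4. Worked example (dates assumed).** Scans are due every 12 weeks, "while on study protocol treatment beginning at Week 12" (SAP 1.3.2.1), so on Days 85, 169 and 253. The SAP formula is PFS in months = (date - first intake + 1) / 30.4375; with first intake on Day 1, Day d gives d / 30.4375. Take the last on-treatment scan at Day 85 and the last dose at Day 100. The visit window is Day 100 + 30 = 130 to Day 100 + 45 = 145, and it is missed.

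- Bar applied, no death: censored at 85 / 30.4375 = 2.79 months.
- Imaging continued: next scans at 169 / 30.4375 = 5.55 months and 253 / 30.4375 = 8.31 months. A progression first seen at Day 169 is an event at 5.55 months; under the bar it is never seen.
- Bar applied, death before two scheduled scans are missed, no other therapy: the death is an event under either rule.
- Bar applied, death after the Week 24 and Week 36 scans are both missed: censored at 2.79 months and the death is not counted. This takes the omitted scans as missing scheduled assessments, which the SAP does not spell out.

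**5. How many subjects?** The documents give neither the proportion stopping before progression nor the proportion missing the window. The assumptions are 10-30% for the first and 10-20% of those for the second, applied to the planned 74 in cohort A.

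- Low: 0.10 x 0.10 x 74 = 0.74.
- High: 0.30 x 0.20 x 74 = 4.44.

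That is about 1 to 4 subjects, or 1-6%. SAP Section 5 records that cohort A exceeds 74, so the count scales up slightly.

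**The case against.** The strongest reply is that the sentence was never meant to touch imaging. It sits inside the subsection on one visit. Read narrowly, it tells sites not to perform that visit's efficacy evaluation out of window, and this has real content for a subject who comes late. FKSI-DRS is such an evaluation, since it runs until the End of Study Treatment visit (Protocol 7.3.3). Imaging has its own 12-week schedule and its own follow-up entry in SAP Table 2. Protocol 5.2.3.1 also asks for every effort to perform protocol evaluations unless consent is withdrawn. This makes the narrow reading plausible, perhaps the likelier intention. It does not remove the conflict, because the limit is not written and the term used includes tumour assessments in Section 3.1.

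A second reply is that the consequences are limited. PFS and DOR are secondary endpoints, and Protocol 11.3 excludes statistical testing of secondary endpoints. Subjects who start other anti-cancer therapy are censored before it anyway. A scheduled scan may still fall before the visit window closes. SAP 3.2.1.2 plans supportive PFS analyses: one counts progression or death despite missed scans, one adds non-radiological progression as an event, and one censors at discontinuation for reasons other than progression or death. All of this stands and keeps the point modest. However, these analyses cannot supply a radiographic progression that was never imaged, and they do not cover DOR.

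**Conclusion.** The conflict is real and in current text. It is an unresolved inconsistency between operative instructions. A reader might infer a deliberate design choice to end follow-up, but the repeated imaging rule and the bar's absence from the SAP do not support that.

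Four further inferences are tempting and should not be drawn.

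- That late first responses are lost from the primary endpoint. SAP 3.1.1 counts responses up to 30 days after discontinuation, and the visit is only missed once day 45 has passed. The same section also says assessments before progression are used regardless of discontinuation, so the primary ORR is best called largely, not wholly, unaffected.
- That every affected subject is censored at the last on-treatment scan. Deaths meeting the SAP's conditions still count as events.
- That about 7 subjects (10% of 74) would be affected. This needs a 10% joint probability of stopping before progression and missing the window, for which the documents give no basis.
- That non-attendance reflects poor health, so that the censoring is informative. This is possible, but the documents give no data on it, and a 15-day window can be missed for ordinary scheduling reasons.

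OS is unaffected, because survival status is collected separately. The size of about 1 to 4 of 74 rests wholly on the assumed ranges and applies only where sites followed the literal text. The point merits correction because it affects endpoint ascertainment and costs almost nothing to settle.

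**What to change.** Reconcile Protocol 5.2.2.1 with 5.2.3, 7.3.1 and Table 2 footnote h. Limit the 5.2.2.1 sentence to evaluations specific to the End of Study Treatment visit, for example the FKSI-DRS due at that visit. Add that tumour imaging under the other three provisions continues whether or not the visit was attended.

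If any site applied the literal text, report by cohort how many subjects stopped imaging for this reason, so that readers of PFS and DOR can judge the effect.

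The cost is one sentence of clarification and, if needed, one count in the study report. No scans are added beyond those already required.

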### 5.2.2.2 *Early Study Withdrawal Visit*

All included subjects who prematurely stop the study due to withdrawal of consent will be invited to attend the Early Study Withdrawal visit. Please see the footnotes in [Table 2](#) for details.

### 5.2.3 *Procedures After Study Treatment*

Subjects who discontinue study treatment with cabozantinib will be invited to enter the Post-treatment Follow-up period. All necessary assessments performed after treatment are indicated in [Table 2](#).

For subjects who have discontinued cabozantinib treatment before radiographic disease progression and who have not withdrawn consent, tumour assessment should be performed until radiographic progression confirmed by the Investigator.

